- Mean number of exacerbations (the mean value, the standard deviation) requiring medical attention (outpatient prescription of systemic corticosteroids) in patients with severe asthma at the 2 year of follow-up;

- Mean number of exacerbations (the mean value, the standard deviation) requiring medical attention (outpatient prescription of systemic corticosteroids) in patients with severe asthma at the 3 year of follow-up;
- Mean number of exacerbations (the mean value, the standard deviation) requiring medical attention (outpatient prescription of systemic corticosteroids) in patients with severe asthma at the 4 year of follow-up;
- **Mean number of hospitalizations** (the mean value, the standard deviation) in patients with severe asthma at the time of inclusion in the study;
- Mean number of hospitalizations (the mean value, the standard deviation) in patients with severe asthma at the time of inclusion in the 1 year of follow-up;
- Mean number of hospitalizations (the mean value, the standard deviation) in patients with severe asthma at the time of inclusion in the 2 year of follow-up;
- Mean number of hospitalizations (the mean value, the standard deviation) in patients with severe asthma at the time of inclusion in the 3 year of follow-up;
- Mean number of hospitalizations (the mean value, the standard deviation) in patients with severe asthma at the time of inclusion in the 4 year of follow-up;
- **Percentage of patients with severe asthma** (the mean value, the standard deviation) taking high doses of **ICS/LABA, ICS/LABA+LAMA as maintenance therapy, biologics** at the time of study enrollment;
- Percentage of patients with severe asthma (the mean value, the standard deviation) taking high doses of ICS/LABA, ICS/LABA+LAMA as maintenance therapy, biologics at the 1 year of follow-up;
- Percentage of patients with severe asthma (the mean value, the standard deviation) taking high doses of ICS/LABA, ICS/LABA+LAMA as maintenance therapy, biologics at the 2 year of follow-up;
- Percentage of patients with severe asthma (the mean value, the standard deviation) taking high doses of ICS/LABA, ICS/LABA+LAMA as maintenance therapy, biologics at the 3 year of follow-up;
- Percentage of patients with severe asthma (the mean value, the standard deviation) taking high doses of ICS/LABA, ICS/LABA+LAMA as maintenance therapy, biologics at the 4 year of follow-up;

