### **3.7. Registry Follow-up**

Since the study is in the form of a Registry - non-interventional observational study - there is no planned intervention in the common clinical practice of patient management, the number of follow-up visits will be based on existing recommendations and protocols for managing patients with asthma in the Russian Federation and the patient's needs. It is assumed that the patient will visit health facilities once in 3 months. The frequency of visits depends on the initial level of control of asthma in the patient, the response to treatment.

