## 9. APPENDIX: Main variables

	Category	Variable's Fields Names	Response options (if applicable)
1	Inclusion Criteria	Is the patient suffering from uncontrolled asthma and taking medium-to-high doses of ICS?  Please check one of the following:  1. At the stage 5 GINA  2. (a) Uncontrolled in Stage 4: There are symptoms of severe asthma  2. (b) Uncontrolled in stage 4: there are exacerbations requiring OCS	No/Yes
2	Inclusion Criteria	The patient meets the criteria for the inclusion in RSAR	No/Yes
3	Detailed description of the patient	Visit date	DD / MM / YYYY
4	Detailed description of the patient	Date of Birth  Age at the moment of examination	DD / MM / YYYY  Full age (calculated automatically)
5	Detailed description of the patient	Gender	Male/female
6	Detailed description of the patient	Race	Caucasian / Southeast Asian / Northeast Asian / African / Mixed / Other
7	Detailed description of	IIIT	Decimal number (calculated automatically)

	the patient		
8	Detailed description of the patient	BMI	Decimal number (calculated automatically)
9	Detailed description of the patient	Height	Decimal number
10	Detailed description of the patient	Weight	Decimal number
11	Detailed description of the patient	Was the bronchial thermoplastics given to the patient?	No/Yes
12	Occupation	What is the current patient's occupation?	Free text entry
	Occupation	Occupational risks	- at the moment; - in anamnesis.
13	Anamnesis	What is current smoking status of a patient?	Never smoked / Former smoker / Currently smokers
14	Anamnesis	-Number of cigarettes smoked daily? (if marked "ex-smoker", "currently smokes")	Number
15	Anamnesis	-Years of smoking? (please indicate the period of time during which the patient smoked continuously)	Number
16	Anamnesis	-Pack-Years	Number (calculated automatically)
17	Anamnesis	-Years, passed after you quit smoking?  (please specify the time period from which the patient stopped smoking)	Number

18	Anamnesis	At what age did the symptoms of asthma start to appear in the patient?  Full years or months, if <1 year	Number
19	Anamnesis	Number of exacerbations requiring treatment with systemic glucocorticosteroids in the last 12 months?	Number
20	Anamnesis	The total number of episodes of invasive pulmonary ventilation?	Number
21	Anamnesis	Total number of ambulance calls due to asthma in the last 12 months?	Number
22	Anamnesis	Total number of hospitalizations due to asthma in the last 12 months?	Number

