23	Anamnesis	Indicate the number disability episodes in the last 12 months (for BA).	Number
24	Significant concomitant diseases	Atopic dermatitis  Atopic disease: yes, if atopic dermatitis is noted	Never / in the past / currently
25	Significant concomitant diseases	Allergic rhinitis  Atopic disease: yes, if allergic rhinitis is noted	Never / in the past / currently
26	Significant concomitant diseases	Non-allergic rhinitis	Never / in the past / currently
27	Significant concomitant diseases	Chronic rhinosinusitis with polyps	Never / in the past / currently
28	Significant concomitant diseases	Chronic rhinosinusitis without polyps	Never / in the past / currently

29	Treatment of significant concomitant diseases	Atopic dermatitis Allergic rhinitis Non-allergic rhinitis Chronic rhinosinusitis with polyps Chronic rhinosinusitis without polyps	Indicate treatment of significant concomitant diseases
30	Significant concomitant diseases	Indicate concomitant diseases in the patient	obesity, - Type 2 diabetes, - Arterial hypertension, - IHD, - COPD, - CHF, - CRF; other.
31	Treatment of significant concomitant diseases	obesity, - Type 2 diabetes, - AH, - IHD, - COPD, - CHF, - CRF; other.	Indicate treatment of significant concomitant diseases
32	Blood/ sputum	What was the largest number of eosinophils of blood (over the last year)?	Decimal number
33	Blood/ sputum	- Date of the maximal number of eosinophils of blood (for the last year)	DD / MM / YYYY

34	Blood/ sputum	-Was the greatest number of eosinophils of blood recorded during exacerbation?	No/Yes
35	Blood/ sputum	What was the maximal number of eosinophils of the blood? (for the last year and beyond the exacerbation)	Decimal number
36	Blood/ sputum	Date of the maximal number of eosinophils of blood (for the last year and without exacerbation)	DD / MM / YYYY
37	Blood/ sputum	Current (last) value of eosinophils	Decimal number
38	Blood/ sputum	-Last date of eosinophils measurement	DD / MM / YYYY
39	Blood/ sputum	What was the maximal number of eosinophils in sputum (over the last year)? (in percentages)	Decimal number
40	Blood/ sputum	- Date of the maximal number of eosinophils of blood (for the last year)	DD / MM / YYYY
41	Blood/ sputum	What is the current IgE value (last)?	Decimal number
42	Blood/ sputum	- Date of current IgE measurement (latest)	DD / MM / YYYY
43	Blood/ sputum	Was the patient's periostin level measured?	- Yes; - No;
45	Diagnostics	Was chest radiography performed?	Normal/ Abnormal/Was not performed

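### The year-1 to year-4 event endpoints have no enrolment-anchored window: the only count fields shown look back 12 months from visits whose timing the protocol does not fix

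*Combined protocol and SAP*

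**What the plan says.** Section 2.2 names the exacerbation categories (1, 2, 3 or more), the mean number of exacerbations, hospitalisations, emergency calls and disability sheets for each of years 1 to 4. The mean exacerbation count, for example, is for events "requiring medical attention (outpatient prescription of systemic corticosteroids) in patients with severe asthma at the 4 year of follow-up". The hospitalisation objective leaves its period unclear: "hospitalizations (the mean value, the standard deviation) in patients with severe asthma at the time of inclusion in the 1 year of follow-up".

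The Appendix of main variables shows one count field for each kind of event. Item 19 is "Number of exacerbations requiring treatment with systemic glucocorticosteroids in the last 12 months", item 21 is "Total number of ambulance calls due to asthma in the last 12 months", item 22 is "Total number of hospitalizations due to asthma in the last 12 months", and item 23 asks for disability episodes over the same period. All four look back from the visit. None has a date field beside it, although many laboratory, lung-function and drug items in the same Appendix do.

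On visits, section 3.7 says "It is assumed that the patient will visit health facilities once in 3 months" and then "The frequency of visits depends on the initial level of control of asthma in the patient, the response to treatment". Section 3.3 adds that data are also collected when a patient is hospitalised. No section defines an anniversary visit, a window around it, or which visit supplies a given year.

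**The concern.** A 12-month look-back equals a follow-up year only if it is taken on the anniversary of enrolment. Taken earlier in the first year, it carries events from before entry into year 1. In later years, successive look-backs may count some months twice and miss others.

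The pre-enrolment year is not a neutral one to borrow from. One entry route (section 3.5, second footnote) requires at least two systemic steroid courses in the past year, so the rate before entry may well exceed the rate after it. Overlap would then raise year-1 counts and hide part of any fall after enrolment, in a registry that section 2.0 says is meant to evaluate pharmacotherapy. Because visit timing depends on control and response, the error could also differ between well and poorly controlled patients.

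**Working it through.** The documents give no event rate or precision figure for these endpoints, so there is no figure of the plan's own to reproduce. The event rates below are assumptions.

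**Inputs from the documents.** Look-back of 12 months (Appendix, items 19 and 21 to 23); assumed visit interval of 3 months (section 3.7); inclusion and observation both ending 11.2022 (section 3.1); 1,000 of 7,000 planned CRFs in 01.2022 to 11.2022 (section 3.2).

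**Overlap in year 1.** A look-back at month t < 12 contains a pre-enrolment share of (12 − t)/12. With rates *pre* and *post*, the reported mean is pre × (12 − t)/12 + post × t/12. The relative bias is therefore (12 − t)/12 × (pre/post − 1).

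With pre = 3.0 and post = 1.5:
- Month 10.5: 0.125 × 3.0 + 0.875 × 1.5 = 1.69, or +12.5%.
- Month 9: 0.25 × 3.0 + 0.75 × 1.5 = 1.88, or +25%.
- Month 6: 0.50 × 3.0 + 0.50 × 1.5 = 2.25, or +50%.

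**Visit nearest month 12.** Take visits exactly 3 months apart, with the anniversary falling at random between them. The nearest visit is then uniform within ±1.5 months of month 12. Mean overlap is (1.5²/2)/3 = 0.375 months, a share of 0.375/12 = 3.1%. At the rates above the average bias is 3.1% × (2 − 1) = +3.1%, with a maximum of 12.5% at month 10.5. If visits fell exactly at months 3, 6, 9 and 12 from enrolment, the bias would be zero.

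**Range over assumed rates (bias in the year-1 mean):**

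| Look-back taken as year 1 | Mean overlap, months | 2.0 → 2.0 | 2.0 → 1.5 | 3.0 → 1.5 | 2.0 → 0.5 |
|---|---|---|---|---|---|
| Nearest to month 12 | 0.375 | 0% | +1.0% | +3.1% | +9.4% |
| Last visit within year 1, 3-month spacing | 1.5 | 0% | +4.2% | +12.5% | +37.5% |
| Month 9 | 3 | 0% | +8.3% | +25% | +75% |
| Month 6 | 6 | 0% | +16.7% | +50% | +150% |

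Only the ratio of the rates matters for the mean, so 2.0 → 1.0 gives the same percentages as 3.0 → 1.5. For the categories, under a Poisson distribution with rates 2.0 and 1.0, the share with 3 or more exacerbations is 8.0% when year 1 is measured correctly, 13.2% from a month-9 look-back and 19.1% from a month-6 look-back.

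**Later years.** If month 10.5 supplies year 1 and month 25.5 supplies year 2, the second look-back covers months 13.5 to 25.5, and months 10.5 to 13.5 are missed. If months 13.5 and 22.5 are used, the look-backs cover 1.5 to 13.5 and 10.5 to 22.5, and 3 months are counted twice. Neither case brings in pre-enrolment time.

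**Late enrolment.** A patient enrolled in January 2022 has at most 11 months before the end of 11.2022. Every follow-up look-back for patients enrolled in 2022 therefore has a pre-enrolment share of at least 1/12 = 8.3%. The 2022 recruitment target is 1,000/7,000 = 14.3% of the planned total.

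**Event-driven visits.** The zero in the 2.0 → 2.0 column also needs visit timing to be unrelated to events. A look-back recorded at an admission contains that admission. At a constant Poisson rate of 1 per year, for illustration, a 12-month window ending at an event contains 1 + 1 = 2 expected events.

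**The case against.** The strongest reply is that ordinary practice would contain the problem. Visits are assumed 3-monthly, item 112 records the next visit date with reminders, section 4.8 has a missed planned visit trigger contact, and item 3 records the visit date. An analyst who took the visit nearest each anniversary would see about 1% to 9% bias under the changing rates tabulated. This stands as far as it goes, but the plan does not state that rule.

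It is also fair that the use of items 19 and 21 to 23 at follow-up is an inference. The Appendix files them under history. Section 5.2 mentions an extended variable list, and section 4.8 promises clarifying questions on time intervals; neither is shown. However, if these items are for enrolment only, no field shown supplies the annual endpoints.

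A reader might infer several stronger things that the documents do not support:
- That the counts rest on patient recall. Section 3.3 names outpatient cards and case histories as the source.
- That visits are unscheduled. They are planned within routine care, though not fixed by protocol.
- That pre-enrolment events contaminate all four years. With one look-back per year taken near its anniversary, only year 1 is exposed.
- That visits at months 9 and 16 leave the early months uncounted. Together they cover months −3 to 16, and months 4 to 9 are counted twice.
- That quarterly reports would be summed and events multiplied. No section plans this.
- That every patient is selected for frequent exacerbations. GINA step 5 patients, and step 4 patients with symptoms or airflow limitation, can enter without them.

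**Conclusion.** The point holds as a gap in definition and data collection that can bias the year-1 counts and misalign later years. It does not show that the annual counts are biased. The size depends on a rule the plan does not give: at assumed rates of 3.0 before and 1.5 after entry, about +3% on average (maximum 12.5%) with the nearest visit, and +25% or +50% if a month-9 or month-6 visit stands for year 1. The rates are assumptions. If they do not change at entry and visit timing is unrelated to events, the bias is zero.

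For patients enrolled in 2022 overlap is unavoidable if they are given a year-1 value from these items. The primary endpoint (section 2.1) is measured at enrolment, where a 12-month look-back fits, and is not affected. The change should be made because the affected endpoints are a large part of section 2.2 and the remedy is cheap.

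**What to change.** Keep the 12-month items at enrolment only. At follow-up visits, replace items 19 and 21 to 23 with events since the last registry visit, with the date of each event. Assign events to years counted from enrolment (months 0 to 12, 12 to 24, 24 to 36, 36 to 48). Report the 1, 2, 3-or-more categories for patients whose year is fully observed, and events per patient-year for all patients, including incomplete years. A rate alone would not give the listed categories.

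For data already collected without event dates, pre-state that the visit nearest each anniversary, within a fixed window and identified from item 3, supplies that year. Do not use a look-back outside the window as that year's value. This also keeps early look-backs of patients enrolled in 2022 out of year 1.

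The cost is an eCRF wording change, date fields, an analysis rule and slightly more data entry.

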## **1.2. Rationale.**

The development of the Russian Severe Asthma Registry is aimed on supervising current problems that can be encountered when using separate registries for this nosology. Standardization of data collection will help to streamline interoperable sources of data on severe asthma across Russia, as well as to establish an accurate process for researchers to gain access to the Registry, which will collect data and use them in SA patient's management. Data on biomarkers such as FeNO, eosinophils, and IgE will be an important resource in the RSAR, helping to identify patients who are more likely to respond to biological agents.

An example of a successfully implemented observational study is the National Register of Patients with Idiopathic Pulmonary Fibrosis in the Russian Federation, a prospective observational study of idiopathic pulmonary fibrosis (IPF) in the Russian Federation, which was initiated in 2016 by the Russian Respiratory Society in conjunction with the Regional United Medical Informatization System. This innovative project was developed to study the features of epidemiology and the course of IPF, classified as rare diseases (ICD-10 code J84.1 - idiopathic pulmonary fibrosis) in the Russian Federation. It allows to obtain accurate epidemiological data on this nosology, to cooperate specialists from various specialties: pulmonologists, morphologists, radiation diagnostics specialists, and other experts at the federal and regional levels to improve the diagnosis and management of IPF. The Registry allows to achieve significant improvement in the physician's awareness about IPF and to reveal their interest in this problem. So, on the 01.09.2017, 185 doctors from 58 regions of the Russian Federation take part in the Registry, of which:

- 25 major freelance specialists-pulmonologists of the Ministry of Health of the Russian Federation;
- 57 scientists (professors, MD, PhD);

- 51 head of profile departments of state federal, regional and city health care institutions.

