46	Diagnostics	Was chest computer tomography performed?	Normal/ Abnormal/Was not performed
47	Diagnostics	-Date of chest computer tomography	DD / MM / YYYY
48	Diagnostics	Was densitometry done?	No/Yes
49	Diagnostics	Date of densitometry	DD / MM / YYYY

50	Lung function	FEV1 before broncholytic	Decimal number
51	Lung function	FEV1 after broncholytic	Decimal number
52	Lung function	Functional Vital capacity before broncholytic	Decimal number
53	Lung function	Functional Vital capacity after broncholytic	Decimal number
54	Lung function	Prognosed FEV1	Decimal number (calculated automatically)
55	Lung function	FEV1 before broncholytics (% of prognosed)	Decimal number (calculated automatically)
56	Lung function	FEV1 after broncholytics (% of prognosed)	Decimal number (calculated automatically)
57	Lung function	Prognosed FVC	Decimal number (calculated automatically)
58	Lung function	FVC before broncholytics (% of prognosed)	Decimal number (calculated automatically)
59	Lung function	FVC after broncholytics (% of prognosed)	Decimal number (calculated automatically)
60	Lung function	The ratio of FEV1 / FVC before bronchodilator	Decimal number (calculated automatically)
61	Lung function	The ratio of FEV1 / FVC after bronchodilator	Decimal number (calculated automatically)
62	Lung function	Spirometry	DD / MM / YYYY
63	Lung function	Was the test for methacholine PC20 / histamine/exercise performed?	No/Yes
64	Lung function	-Date of PC20 test	DD / MM / YYYY
65	Lung function	- PC20 result	Decimal number (calculated automatically)
66	Lung function	An exhaled nitric oxide test was performed?	No/Yes

67	Lung function	- Date of analysis for expired nitric oxide	DD / MM / YYYY
68	Lung function	- Results of the analysis for expired nitric oxide	Decimal number (calculated automatically)
69	Allergic tests (ALL)	Was the environmental allergens test performed?	Determination of specific IgE in blood/Scarification test/Was not done
70	Allergic tests (determination of specific IgE in blood)	- Date of determination of specific IgE in blood	DD / MM / YYYY
71	Allergic tests (determination of specific IgE in blood)	- Was specific IgE in blood positive for year-round allergens?	No/Yes
72	Allergic tests (determination of specific IgE in blood)	+ Indicate the year-round allergens to which specific IgE in blood was positive (select all applicable)	Dust mite (eg D. Pteronyssinus) / cat's hair / mixture of molds / dog hair / aspergillus / other (please specify)

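### As listed in the appendix, the FeNO and PC20 results are derived fields with no numeric input, the challenge test used is not recorded, the sputum eosinophil date carries a blood label, and onset age has no unit

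*Combined protocol and SAP*

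**What the plan says.** All the fields are in section 9, the appendix of main variables.

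- **PC20.** Item 63 asks "Was the test for methacholine PC20 / histamine/exercise performed" and takes No/Yes. Item 64 is "Date of PC20 test". Item 65 is the result, with the response type "Decimal number (calculated automatically").
- **FeNO.** Item 66 asks whether the test was done ("An exhaled nitric oxide test was performed", No/Yes) and item 67 gives its date. Item 68 is "Results of the analysis for expired nitric oxide", with the same automatic response type as item 65.
- **Sputum eosinophils.** Item 39 is the highest sputum percentage over the last year. The date field directly beneath it, item 40, reads "Date of the maximal number of eosinophils of blood (for the last year"), which is also the wording of item 33, the date of the blood maximum.
- **Onset age.** Item 18 asks for age at first symptoms as "Full years or months, if <1 year". The response is a single number with no unit field.

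On the use of these data, section 1.2 says: "Data on biomarkers such as FeNO, eosinophils, and IgE will be an important resource in the RSAR". Section 2.0 includes determining severe-asthma phenotypes in the overall objective. Section 3.4 lists blood eosinophils, sputum eosinophils, IgE and FeNO as the biomarkers to be collected where possible. It also says that data from existing registries may be brought in and sorted to the registry's standard fields.

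**The concern.** FeNO and PC20 are measurements read from a test report. They cannot be computed from a yes/no answer and a date. A field specified as derived, with nothing to derive it from, invites a build in which the investigator cannot type the value. The record would then show that a test was done and when, but not what it found.

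The other three defects concern meaning:

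- PC20 is a provocative concentration. An exercise challenge gives no such value, so a Yes at item 63 with an empty item 65 could be a correct record or a missing result, and a filled item 65 does not say which agent was used.
- A sputum value that is a maximum over 12 months needs its own date. Under a blood label, some sites may enter the sputum date and others the blood date.
- An onset age whose unit is unknown cannot separate infant onset from onset in childhood.

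At stake is the biomarker and phenotype work that sections 1.2 and 2.0 give as reasons for the registry. Imported registry data mapped to the same definitions would inherit the same faults.

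**Working it through.** The documents give no figure to reproduce. The check has two parts: trace the inputs of every automatic field, then compare labels and units.

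**1. Input tracing.** Fourteen items carry an automatic response: 4 (age), 7, 8, 16, 54 to 61, 65 and 68.

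| Item | Derived value | Listed inputs |
|---|---|---|
| 4 | Age | Birth date (4), visit date (3) |
| 8 | BMI | Height (9), weight (10) |
| 16 | Pack-years | Cigarettes per day (14), years smoked (15) |
| 54, 57 | Predicted FEV1, FVC | Can be derived from age, sex, race, height (4, 5, 6, 9) |
| 55, 56, 58, 59 | Percent predicted | Items 50 to 54 and 57 |
| 60, 61 | FEV1/FVC | Items 50 to 53 |
| 65 | PC20 | None: a flag (63) and a date (64) |
| 68 | FeNO | None: a flag (66) and a date (67) |
| 7 | Label not legible in the available text | Not assessed |

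So 1 + 1 + 1 + 2 + 4 + 2 = 11 items have traceable inputs, one cannot be judged, and two have no numeric input. The list does distinguish entered from derived values: blood eosinophils (32, 35, 37), sputum eosinophils (39) and IgE (41) are plain decimals. Items 65 and 68 are of that kind but carry the other response type.

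**2. Labels.** Item 33 follows a blood value (32) and names blood. Item 40 follows a sputum value (39) and also names blood. Item 42 follows IgE (41) and names IgE. Item 40 is the odd one out, and no date field in the list names sputum.

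**3. Units of onset age.** Onset at m months is entered as m, for m = 1 to 11. Read as years, the error is m − m/12 = 11m/12 years:

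- m = 1: 11/12 = 0.9 years
- m = 11: 121/12 = 10.1 years
- mean over m = 1 to 11: (11/12) × 6 = 5.5 years

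An entry of 6 may mean 6 years or 0.5 years, a ratio of 12. Patients must be at least 12 years old (section 3.5), so every value from 1 to 11 is below current age in either unit. A programmed range or logic check of the kind described in section 4.2 would not detect the confusion.

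The documents do not give the share of patients with onset before 1 year. If it were 1% to 5% (an assumption), reading all such entries as years would raise the mean onset age by 0.01 × 5.5 = 0.055 to 0.05 × 5.5 = 0.275 years. The mean would hardly move; the damage would be misclassification within the early-onset group.

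**The case against.** The strongest reply is that the appendix is a list of variables and not the eCRF build. The eCRF is a separate document for ethics submission (section 5.4), data-collection specifications sit in a separate data management plan (section 4.2), and section 5.2 describes an extended list that includes severe-asthma biomarkers. None of these is available here, and nowhere do the documents say that automatic fields are closed to entry. A slip is also the likelier cause: the automatic response type runs through items 54 to 61 just above and could easily have been carried down in a translated table. All of this stands. A reader might infer that FeNO and PC20 results are lost for every patient tested; the documents support only that they may be, if the fields were built as listed.

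Item 40 is a sub-field placed directly under the sputum value, and the blood date already exists at item 33, so its position shows what was meant. A date can be entered. A reader might conclude that no sputum sample is dated, but the text supports only a wrong label and the uncertainty it brings.

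It is also tempting to call onset age the registry's only information on disease duration. Section 4.4 defines newly identified patients by time since diagnosis, and the screening log in section 4.8 appears to hold a diagnosis date, so that reading fails.

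Finally, none of the objectives in sections 2.1 and 2.2 uses FeNO, PC20, sputum eosinophils or onset age, and biomarkers are collected only where possible. This limits the importance of the point but does not remove it: the appendix is the protocol's own statement of its main variables, and it should be right in itself.

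**Conclusion.** The point holds for the fields as specified in the appendix. Two result fields (65 and 68) have no numeric source, one field (63) does not identify the test behind the result, one date (40) is mislabelled, and one number (18) has no unit for entries 1 to 11, with an error of 0.9 to 10.1 years for each infant-onset patient read as years.

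Whether FeNO and PC20 values are in fact missing depends on how the eCRF was built, which the documents do not show. The ambiguity at item 18 likewise assumes that the built field has no unit. The number of patients affected by any of these defects is unknown.

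No listed primary or secondary result would change; the IgE and blood eosinophil fields that the secondary objectives need are ordinary entered decimals. The effect is on the biomarker and phenotype purpose in sections 1.2, 2.0 and 3.4. The corrections should be made because they are simple and because lost units and values become harder to recover as records accumulate towards the planned 7,000. The point does not threaten the main analysis.

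**What to change.** First compare the built eCRF with the appendix, since this decides how much has gone wrong in practice. Then:

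- **Items 65 and 68:** make both entered decimals with a stated unit (ppb for FeNO).
- **Item 63:** record which test was done (methacholine, histamine or exercise). Open item 65 only for methacholine or histamine, and tabulate PC20 by agent.
- **Item 40:** relabel as the date of the maximal sputum eosinophil value.
- **Item 18:** add a years/months selector and store the value in years.
- **Existing records:** query item 18 entries of 1 to 11, and any blank FeNO or PC20 result where the test is marked as performed.

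The specification changes are minor: five fields, with no new procedure for patients. The query workload depends on the build. If the result fields accepted typed values, it is small. If they did not, recovering FeNO and PC20 means returning to source records at up to 100 facilities for patients who were tested.
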